4.1 CultureCoin

The 16-well CultureCoin (**Figure 2**) is a standard size (60mm) embryo culture dish with individual micro-wells aligned in a row in the center of the dish. Each micro-well is designed to accommodate a single patient's oocytes or developing embryos through the blastocyst stage and are culture individually. The 16-well CultureCoin is designed to fit in only one (1) position in one (1) of the individual six (6) incubator chambers, and each micro-well is identified to facilitate embryo tracking (for example, micro-well

Figure 2: CultureCoin

5. Number of Centers and Study Duration

The TiMMI study will include only one investigational site. This site will conduct the study under a single clinical investigation plan.

Expected study duration is 18 months including enrollment and follow-up. Subjects will be followed until pregnancy outcome has been determined (i.e. date of negative hCG test or 8-12 week clinical pregnancy ultrasound, if pregnant).

6. Study Design

This is a prospective, non-blinded, observational, randomized, double-arm study.

7. Statistical Methods and Analyses

Up to 500 subjects' embryos will be collected in this ongoing data collection protocol. We aim to recruit 200 patients in the standard culture group, and 300 patients in the MIRI-TL group.

Assuming that 25% of all inseminated oocytes would develop into blastocysts (based on published clinical data), at least 1300 inseminated oocytes (~163 patients) would be needed in each group to detect an increase in blastocyst proportion of 20% with 80% power and a significance level of 0.05 (two-tailed tests).

Assuming that time from insemination to start of blastulation (tSB) follows a normal distribution, and is 96h with a variance of 49h in euploid embryos, and 98h (variance 49h) in aneuploid embryos, ~405 blastocysts (1620 inseminated oocytes = 203 patients) in the MIRI-TL group will need to be biopsied to detect a significant difference in tSB (80% power, 0.95 confidence level, 2-tailed test). Since ~80% of all patients receive PGS at our clinical site, we will need ~255 patients in our MIRI-TL group.

To account for patient dropout and lower than expected oocyte retrieval per patient, we propose to recruit up to 500 subjects in this ongoing data collection protocol: 200 patients in the standard culture (SC) group and 300 patients in the MIRI-TL (MIRI) group.

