Embryos with incomplete annotations will be excluded from analysis. All variables will be tested for normality using Shapiro–Wilks test. Continuous data following a normal distribution will be analyzed with Students t-test.

Continuous data not fulfilling the assumption of normality will be analyzed with non-parametric tests such as the Wilcoxon rank-sum test. For categorical data Chi-squared or Fisher's exact test will be used. Two-tailed p-values < 0.05 will be considered significant.

8. Study Protocol

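### A normality pre-test decides which hypothesis is tested for each continuous variable, so the powered tSB comparison may not estimate the 2 h mean difference it was sized on

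*Combined protocol and SAP*

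**What the plan says.** The last two paragraphs of Section 7 (Statistical Methods and Analyses) give a general rule and no endpoint-specific analysis. The pre-test is universal: "All variables will be tested for normality using Shapiro–Wilks test". If normality is accepted, "Continuous data following a normal distribution will be analyzed with Students t-test". If not, "Continuous data not fulfilling the assumption of normality will be analyzed with non-parametric tests such as the Wilcoxon rank-sum test". Significance is fixed by "Two-tailed p-values < 0.05 will be considered significant".

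The text does not give the level of the Shapiro-Wilk test. It does not say whether the test is run per group, on pooled data or on residuals. The fallback is introduced only by example, and no effect measure is named for any continuous outcome.

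Earlier in the same section, the tSB sample size assumes that tSB "follows a normal distribution, and is 96h with a variance of 49h in euploid embryos", against 98 h with the same variance in aneuploid embryos. The total is about 405 biopsied blastocysts from about 203 patients in the MIRI-TL group.

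The other powered outcome, the blastocyst proportion, falls under a different sentence, "For categorical data Chi-squared or Fisher's exact test will be used", and is not touched by the pre-test.

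**The concern.** The two branches answer different questions. Student's t-test addresses a difference in means, in hours. The rank-sum test addresses whether values in one group tend to exceed those in the other, and it gives no difference in mean hours. If the data choose the branch, the plan has not said before seeing them what the tSB comparison will estimate.

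The choice also turns on the wrong feature. With about 400 observations, Shapiro-Wilk detects departures too small to disturb a comparison of means. Neither branch deals properly with unequal variances, which can disturb it. The gaps in the rule mean that two analysts could follow Section 7 faithfully and report different tests on the same data.

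**Working it through.** **1. The plan's own figure.** Inputs from Section 7: difference 98 − 96 = 2 h, SD √49 = 7 h, 80% power, two-sided 5%. For two equal groups, n per group = 2(1.960 + 0.842)² × 49 / 2² = 192.3, so 193 per group and 386 in total. Dividing by 3/π = 0.955, the efficiency of the rank-sum test on normal data, gives 386 / 0.955 = 404. A t-test with a 1.5:1 split gives about 403. Both are close to 405. The plan does not name its formula, so nothing firm follows about which test was meant. On either route the planned effect is 2 h with SD 7 h.

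**2. What each branch would report.** Under the planned normal distributions, the t-test targets 2 h. The rank-sum test targets the probability that an aneuploid embryo is later than a euploid one: Φ(2 / (7√2)) = Φ(0.202) = 0.58, against 0.50 under the null. Once shapes or variances differ, that probability has no fixed relation to a mean difference in hours.

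**3. How often the switch occurs.** Assumptions: 243 and 162 blastocysts, Shapiro-Wilk at 5%, equal SDs, normal or centred gamma data. The ranges cover repeated simulations, per group and pooled.

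| Skew | Shapiro-Wilk rejects |
|---|---|
| 0.28 | 47–53% |
| 0.45 | 86–91% |

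The t-test did not need replacing in these settings. Its type I error was 4.5% and 5.9% in 4,000 trials each, where the simulation standard error is √(0.05 × 0.95 / 4,000) = 0.34 points. In larger runs (20,000 per case) with the same distribution in both groups, a single t-test gave 4.0–5.3%.

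The undefined unit of the pre-test matters too. For exactly normal data with SDs 6 and 10 h, it rejects in 10% of trials per group but 58% pooled.

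**4. Type I error, same distribution in both groups.** Over ten distribution shapes and group sizes 203/202, 162/243, 300/200 and 20/20 (20,000 runs each), the two-stage rule gave 4.6–5.3%. A single pre-specified rank-sum test gave 4.5–5.3%.

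**5. Type I error, unequal variances.** Assumptions: equal means, 243:162, SD 6 h in the larger group and 10 h in the smaller. The ranges cover repeated simulations; single values are from one.

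| Skew | Two-stage rule | Student's t alone | Rank-sum alone | Welch |
|---|---|---|---|---|
| 0 | 6.0–8.1% | 7.7% | 7.0% | 4.4–5.2% |
| 0.28 | 7.2–7.7% | – | – | 4.5–4.7% |
| 0.45 | 9.2–10.0% | 7.2–7.6% | 9.1–9.9% | 4.9–5.2% |

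Within any one simulation, the rule's rate is within a few tenths of a point of the worse component test, or below it.

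The result depends on the inputs:
- SDs 6.5 and 7.5 h, same split: 5.2–5.6%.
- SDs 6 and 8 h, same split: 6.2–7.1%.
- SDs 6 and 10 h, larger SD in the larger group: 3.3–6.6%.
- SDs 6 and 10 h, groups of 203 and 202, skew 0.45: 8.0–8.3%, against 4.8% for Welch.

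**6. Power in the planned case.** With SD 7 h, a 2 h difference and independent values, three simulations gave 80.0%, 80.8% and 81.4% for the two-stage rule, against 80.1%, 80.9% and 81.6% for Welch.

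**The case against.** A reader might infer that the pre-test itself doubles the stated 5% error rate. The documents do not support that. They state no error rate for the two-stage rule, and they assume a variance of 49 in both ploidy groups, under which the overall error stays at about 5%. SDs of 6 and 10 h mean variances of 36 and 100, a 2.8-fold ratio that appears nowhere in the plan, and the ploidy split is not given either. In that setting Student's t and the rank-sum test are inflated on their own, so deleting Shapiro-Wilk and keeping Student's t would not cure it. Part of the rank-sum figure is also definitional: equal means is not that test's null hypothesis. All of this stands, and the error rate is therefore a secondary, conditional point.

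The reach is also limited. The primary objective (Section 3.1) is to collect safety and imaging data. The blastocyst proportion is unaffected. The powered tSB comparison lies within the MIRI-TL group and is not a comparison of randomised arms. That keeps the point minor.

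It would also go too far to say that the remedy is free. Equal power was shown for Welch on independent values. The model suited to several embryos per patient was not simulated.

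None of this answers the main point, that the tSB analysis and its effect measure are not fixed in advance.

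**Conclusion.** The point holds as a minor one. Section 7 leaves the hypothesis and effect measure for every continuous variable to a test on the same data. For tSB, a harmless skew of 0.28 to 0.45 would move the analysis away from the planned mean difference in roughly half to nine-tenths of trials. That rests on an assumed 243:162 split, an assumed 5% pre-test level and gamma-type skew.

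The overall type I error is about 5% under the plan's own equal-variance assumption. It is about 7 to 10% only if the smaller group is clearly more variable (assumed SDs 6 and 10 h). The cause there is the sensitivity of both component tests to unequal variance, which Welch's test avoids.

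**What to change.** In Section 7, delete the Shapiro-Wilk selection step and name one method for each continuous endpoint.

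- **tSB:** the difference in mean hours between euploid and aneuploid embryos with a 95% CI, allowing unequal variances. Use a mixed or cluster-robust model, because about 405 blastocysts come from about 203 patients (405 / 203 ≈ 2 each).
- **Endpoints with one value per patient:** Welch's t-test, with the mean difference and 95% CI.
- **Rank-sum test:** sensitivity analysis only.

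The cost is a few sentences of text and slightly more analysis work, with no change to data collection. Welch's test costs no power in the planned case. The clustered model may give wider intervals than a sizing based on independent blastocysts implies, so its precision should be checked under a stated within-patient correlation before the text is finalised.

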3.2 Secondary Objectives

- To collect enrollment data: demographics, IVF and pregnancy history
- To collect Day 3, Day 5 and Day 6 embryo morphology data
- To collect pregnancy test and live birth outcome data
- To collect pre-implantation genetic screening (PGS) data (if applicable)
- To collect Frozen Embryo Transfer (FET) data (if applicable)

4. Description of Device

The Miri- TL, manufactured by the study sponsor Esco Medical is a closed-system incubator device with built-in visual monitoring system. This closed system incubation system eliminates any environmental disruption and contamination risk by daily handling. The built-in camera has the ability to record cell division kinetics and morphology of developing embryos which can provide more reliable indicators of embryo quality. This novel time-lapse incubator captures images at five (5) minute intervals and its six (6) separate incubation chambers maximizes temperature and gas stability, providing a safe and secure environment for human embryos.

Figure 1: MIRI-TL

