8.0 Patient Randomization

Patients will be randomized to the MIRI-TL group (MIRI) or the Standard culture group (SC) by randomization number generator through www.randomizer.org, using a number set from 1 to 500. Numbers 1-300 will be assigned to the study (MIRI-TL) group while numbers 301-500 will be assigned to the control (Standard Incubator).

8.1 Egg Retrieval and Fertilization-Day 0

Egg retrieval and fertilization follow the standard protocol in place at the clinical site. Insemination, by intracytoplasmic sperm injection (ICSI) will take place on Day 0 (egg retrieval day) following standard protocol currently in place at the clinical site. The fertilized eggs should be free of cumulus cells as much as possible. If the cumulus cells remain in place, they may interfere with the quality of the imaging. Immediately after micro insemination, eggs will be placed in individual wells within a CultureCoin (MIRI group), or a standard culture dish (SC group), and incubated in the MIRI-TL or standard incubator respectively. All eggs will be cultured in the standard fertilization media currently in place at the clinical site. At 20hr after insemination, the MIRI-TL imaging software will be Paused, and all embryos will be examined by the embryologist for successful fertilization (2PN). All normally fertilized eggs will be placed into a new CultureCoin (MIRI group) or standard culture dish (SC group) containing the standard embryo culture media, and incubated in the MIRI-TL or standard incubator respectively.

Once an embryo is assigned a micro-well location, it must remain in the same location throughout the study imaging period. Embryos assigned to the MIRI group will be imaged in the CultureCoin from Day 0 to Day 7. Images of the developing embryos will automatically be captured with the MIRI-TL Microscope. Data collected will include the following:

- Number of eggs inseminated

- Fertilization method
- Total number of fertilized eggs (2PN)

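### Between-arm comparisons are planned with unadjusted tests only, although baseline data that could sharpen them are collected: an optional efficiency gain, not a bias

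*Combined protocol and SAP*

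**What the plan says.** Section 7 (Statistical Methods and Analyses) sets out the whole analysis in a few lines. Normally distributed continuous data go to a t-test and other continuous data to a rank test such as the Wilcoxon rank-sum. For the rest, "For categorical data Chi-squared or Fisher's exact test will be used". No regression, stratified test, ANCOVA or list of covariates appears anywhere in the document.

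The baseline data are described in Section 3.2: "To collect enrollment data: demographics, IVF and pregnancy history". Age is not itemised there, but it is a fair inference from demographics. Section 8.1 also records the number of eggs inseminated.

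Section 8.0 allocates from a single list: "Numbers 1-300 will be assigned to the study (MIRI-TL) group while numbers 301-500 will be assigned to the control (Standard Incubator". No stratification factor is stated, and neither is the point in the cycle at which a patient is randomised.

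The only between-arm comparison with a sample size is blastocyst proportion. Section 7 aims to "detect an increase in blastocyst proportion of 20% with 80% power" from a 25% base and concludes "at least 1300 inseminated oocytes (~163 patients) would be needed in each group".

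**The concern.** The listed tests cannot take a covariate. If female age or IVF history predicts blastocyst formation or pregnancy, part of the patient-to-patient spread could be explained by data already on the case report form. An unadjusted comparison leaves that spread in the error term, and without stratification nothing in the design balances it. The arm effect is then estimated less precisely than it could be with the same patients. A further stake is that the study is non-blinded: if adjustment is wanted later and no covariate was named in advance, the choice of model is open to question.

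This point concerns the randomised comparison of incubators. It does not concern the tSB contrast between euploid and aneuploid embryos, which is not randomised.

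**Working it through.** **1. The plan's own figure.** Inputs from Section 7: 25% control proportion, 20% increase, two-sided 0.05, 80% power. Read as relative, the target is 25% v 30%. The pooled formula is n = [1.96·√(2·0.275·0.725) + 0.842·√(0.25·0.75 + 0.30·0.70)]² / 0.05² = 1251 oocytes per group, or 1291 with continuity correction. The stated 1300 is reproduced. The absolute reading (25% v 45%) needs only 89 to 98 per group, so it is not what was meant. 1300/163 gives about 8 oocytes per patient. No covariate enters this calculation.

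**2. Assumed inputs.** The documents give none of these: age SD 4.5 years; residual between-patient SD 0.45 on the logit scale (variance 0.2025); age slope b from 0 to -0.10 logit per year. From the plan: p = 0.25, m = 8, and 300:200 patients (2400:1600 oocytes).

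**3. Variance saved in a patient-level analysis.**
- Variance due to age: (4.5·b)². Total between-patient variance: σ² = (4.5·b)² + 0.2025. R² = (4.5·b)²/σ².
- ICC on the proportion scale, by linearisation: p(1-p)·σ² = 0.1875·σ².
- Between-patient share of the variance of a patient's mean: 8·ICC/(1 + 7·ICC).
- Variance cut = R² × share.

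Example, b = -0.07: (4.5·0.07)² = 0.0992; σ² = 0.3017; R² = 0.329; ICC = 0.0566; share = 0.453/1.396 = 0.324; cut = 0.329 × 0.324 = 10.7%.

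**4. Power at 25% v 30%.** SE = √[(1 + 7·ICC)·(0.1875/1600 + 0.21/2400)]; power = Φ(0.05/SE - 1.96). For the adjusted analysis SE is multiplied by √(1 - cut).

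| Slope b | R² | ICC | Variance cut | Power, unadjusted | Power, adjusted |
|---|---|---|---|---|---|
| 0 | 0% | 0.038 | 0% | 87.4% | 87.4% |
| -0.02 | 4% | 0.039 | 1.0% | 87.1% | 87.5% |
| -0.04 | 14% | 0.044 | 3.7% | 86.3% | 87.6% |
| -0.07 | 33% | 0.057 | 10.7% | 84.1% | 87.9% |
| -0.10 | 50% | 0.076 | 19.8% | 80.6% | 88.4% |

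Simulation of a patient-level regression with robust standard errors, with and without age (3000 runs per scenario), gave variance cuts of about 0%, 1%, 3-4%, 11% and 19-22%. Where the null was simulated, rejection stayed near 5%. Absolute power differed by a few points between sets of runs, but the gain was stable: 1-2 points at -0.04, 3-4 at -0.07 and about 8 at -0.10.

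**5. Cross-check without slopes.** If covariates explain 10-30% of between-patient variance at ICC 0.05-0.10, the cut runs from 0.10 × 0.296 = 3.0% to 0.30 × 0.471 = 14.1%. As extra patients that is 500/(1 - 0.03) - 500 ≈ 15 up to 500/(1 - 0.141) - 500 ≈ 80.

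**6. Chance imbalance.** The SD of the difference in mean age is 4.5·√(1/300 + 1/200) = 0.41 years. At b = -0.07 that is 0.41 × 0.07 ≈ 0.03 logit.

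**The case against.** The strongest reply is that nothing here is invalid. Under randomisation, a chance difference in age is random error that a correct standard error already covers. A reader might infer from the unadjusted tests that the arm comparison is biased; the documents do not support that.

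A reader might also be tempted to say that this trial forfeits a definite share of its variance, such as 4-19%. That does not follow either. Every input behind such a range is assumed, and it leaves out the cases where age matters little. The top scenario is demanding: -0.10 logit per year means the odds fall by 1 - e^(-1) = 63% over ten years, with age explaining half of the between-patient variance. Nothing in the documents speaks to that.

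Third, the gain is measured against an unadjusted patient-level analysis. Section 7 counts oocytes, and a chi-squared test on oocytes treats siblings as independent, so its nominal standard error is too small, not too wide. It would be wrong to say that the plan's confidence interval is widened; none is specified. The independence assumption is a separate and weightier matter, and correcting it must not be credited to covariate adjustment.

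Finally, Section 3.1 gives data collection as the primary objective, and blastocyst proportion is never named as a primary endpoint.

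All of this stands. It limits the size and urgency of the point but does not remove it: no covariate is pre-specified, allocation is unstratified, and baseline data that could be used are collected.

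**Conclusion.** The point holds as an optional efficiency gain. Under the assumptions listed, adjusting for female age saves between nothing and about 20% of the variance of the arm estimate for blastocyst proportion, with roughly 0 to 9 points of power and no inflation of type I error. The saving is 1% or less if the age effect is nil or weak. Which part of the range applies cannot be settled from the documents. No gain has been quantified for clinical pregnancy, ongoing pregnancy or live birth.

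**What to change.** In Section 7, make the between-arm analysis of blastocyst proportion a pre-specified logistic model with arm and female age (age of the oocyte provider at retrieval, where recorded) and patient-robust standard errors. Report the standardised risk difference with its 95% CI. The marginal estimate matters, because a conditional odds ratio does not gain precision in the way a linear model does.

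Two further covariates are conditional:
- Number of oocytes inseminated, only if randomisation takes place after that number is fixed. Section 8.0 does not say when patients are randomised, so this should be stated first.
- Fresh v frozen oocytes, only if that status is recorded. It is not itemised among the data collected.

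Use the same age adjustment, one record per patient, for clinical pregnancy, ongoing pregnancy and live birth. Keep unadjusted patient-level estimates as supportive.

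The cost is a paragraph of SAP wording and a little programming. No extra patients are needed, and no new data provided that age is captured under demographics, which should be confirmed on the case report form.

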8.2 Day 3 Embryo Assessment

At Day 3, the MIRI-TL imaging software will be Paused and the embryologist will evaluate embryos from both groups per standard procedure. The development stage of the embryos and grading based on traditional morphology criteria will be recorded. It is recommended that the Day 3 morphology assessment is done within 48 hours after the fertilization (2PN) check. ***Per protocol, Assisted Hatching (AH) is allowed if patients have opted for embryo biopsy and PGS.***

After embryo assessment the embryos may be placed back into the MIRI-TL or standard incubator as per their respective groups, and imaging will be resumed for the MIRI group.

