8.3 Day 5, 6 and 7 Embryo Assessment

The embryologist will evaluate the embryos using traditional morphological grading. It is recommended that the Day 5 morphology assessment is done within 48 hours after the Day 3 morphology assessment.

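### If embryo grades are compared between arms in their ordered levels, Section 7's only applicable rule is a test that ignores the order; naming an ordinal method is a cheap gain in sensitivity

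*Combined protocol and SAP*

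**What the plan says.** Section 7 sorts variables into two types. For continuous data it prescribes a t-test when normality holds; otherwise, "Continuous data not fulfilling the assumption of normality will be analyzed with non-parametric tests such as the Wilcoxon rank-sum test". For everything else it has one sentence, which opens "For categorical data Chi-squared or" and gives Fisher's exact test as the alternative. The threshold is common to all tests: "Two-tailed p-values < 0.05 will be considered significant". There is no rule for ordered categories, and Section 7 does not mention embryo grades.

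Grades enter elsewhere. Section 3.2 lists as a secondary objective "To collect Day 3, Day 5 and Day 6 embryo morphology data". Section 8.2, which covers both groups, states: "The development stage of the embryos and grading based on traditional morphology criteria will be recorded". Section 8.3 adds for the later days: "The embryologist will evaluate the embryos using traditional morphological grading". None of these sections gives the grading scale, the number of levels or the coding, and none states a between-arm hypothesis or power for grades.

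**The concern.** A morphology grade is ordered from worse to better. The rank test in Section 7 is confined to continuous data, so a grade kept in more than two levels falls, on the plain reading, under Chi-squared or Fisher. Those tests give the same answer if the grade labels are shuffled. With k levels they spread their sensitivity over k − 1 degrees of freedom, whereas an ordinal test puts it on one degree of freedom aimed at a shift up or down the scale.

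The synopsis gives the study's purpose as showing that the MIRI-TL is at least as safe and effective as standard incubators, and embryo quality by arm is a natural thing to look at for that purpose. A moderate, consistent shift in grades could then be missed, and a non-significant Chi-squared result could be misread as showing no difference in quality. Its p-value also gives neither the direction nor the size of any shift.

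**Working it through.** **The plan's own figure.** The only powered between-arm comparison in Section 7 is the blastocyst proportion: 25% in controls, a 20% increase (read as relative, so 30%), 80% power, two-sided 0.05, at least 1300 oocytes per group.

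- Without continuity correction: n = [1.960·√(2 × 0.275 × 0.725) + 0.842·√(0.25 × 0.75 + 0.30 × 0.70)]² / 0.05² = 1251.
- With it: n/4 × [1 + √(1 + 4/(n × 0.05))]² = 1291, which agrees with 1300.
- An absolute increase (25% v 45%) would need only 89, so the relative reading is the right one.

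This outcome has two levels, so the order of categories plays no part in it.

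**General loss for an ordered grade.** Under a consistent (proportional-odds) shift, the noncentrality λ is almost the same for the Pearson test and the rank test; what differs is the degrees of freedom. For 80% power at 0.05, a 1 df test needs λ = 7.85. Giving that λ to a Chi-squared test on k − 1 df yields:

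| Grade levels | df | Chi-squared power when the ordinal test has 80% | λ needed for 80% | Ratio of sample sizes |
|---|---|---|---|---|
| 2 | 1 | 80% | 7.85 | 1.00 |
| 3 | 2 | 71% | 9.63 | 1.23 |
| 4 | 3 | 65% (64.5%) | 10.90 | 1.39 |
| 5 | 4 | 60% | 11.94 | 1.52 |

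**Embryo counts.** The documents give no number of graded embryos, so a range is used.

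- Section 7 implies 1300/163 ≈ 8 inseminated oocytes per patient. Blastocysts at 25%: 8 × 0.25 × 300 = 600 and 8 × 0.25 × 200 = 400.
- Day 3, lower count: eligibility requires at least 4 normally fertilised embryos, so 4 × 300 = 1200 and 4 × 200 = 800 at full recruitment.
- Day 3, upper count: if all 8 oocytes per patient were graded, 2400 and 1600.

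**Power at those counts.** The formulas are λ(Chi-squared) = (n₁n₀/N) Σ (p₁ⱼ − p₀ⱼ)²/p̄ⱼ and λ(rank) = (n₁n₀/N) [Σ sⱼ(p₁ⱼ − p₀ⱼ)]²/Var(s), where p̄ⱼ is the pooled share in grade j and s is the mid-rank score.

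Example: four even control grades, odds ratio 1.3, 600 v 400. The MIRI-TL distribution becomes 20.4/23.1/26.3/30.2%, and n₁n₀/N = 240. Both noncentralities are 5.14. Power is 45% on 3 df and 62% on 1 df.

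For three assumed control distributions (four even grades, five even grades, and 40/30/20/10%), with embryos treated as independent as in the plan's own sample size, and odds ratio 1.3:

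| Embryos (MIRI-TL v standard) | Chi-squared | Ordinal | Loss |
|---|---|---|---|
| 600 v 400 | 42–45% | 61–63% | 17–21 points |
| 1200 v 800 | 74–77% | 88–90% | 12–16 points |
| 2400 v 1600 | 97–98% | 99–100% | about 2 points (1 with three even grades) |

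The small loss in the last row arises because both tests are near their ceiling. At odds ratio 1.2 with the same counts, four and five even grades give 73–76% v 88–89%.

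**Where the ranking reverses.** If the arms differ as 30/40/30% v 25/50/25% at 600 v 400, Chi-squared has 80% power and the ordinal test 5%, because the average rank does not move.

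**The case against.** A reader might infer that Section 7 assigns embryo grades to Chi-squared and that the between-arm morphology comparison therefore loses a substantial share of its power. The documents do not support that.

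- Section 7 never names grades; the link is an inference from a generic rule.
- The secondary objective is worded as data collection. No between-arm grade comparison is specified and no power is claimed for one, so there is no stated power to lose.
- The scale, the grade distribution and the effect are all absent. The grade might be reduced to two levels, and then nothing is lost. At the larger Day 3 counts and odds ratios of 1.3 or more, the loss can be a few points or less.
- A monotone shift is plausible for an incubator effect, but nothing in the documents says it will take that form, and for a non-monotone change Chi-squared is the better test.
- Ignoring order does not invalidate the test.

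All of this stands as a limit on the size and certainty of the point. It does not remove the point. Both arms are graded, the only rule available for a multi-level grade ignores its order, and if the sponsor intends something else the text does not say so. Clustering of embryos within patients is a separate matter. It would lower the power of both tests, and the figures above leave it out.

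**Conclusion.** The point holds conditionally. If Day 3 or Day 5–7 grades are compared between arms in more than two ordered levels, the plan as written uses a valid but less sensitive test. Under a consistent shift, the loss from 80% power is about 9 points with three grades, 15 with four and 20 with five. In the worked cases at odds ratio 1.3 it runs from about 1 to 16 points at Day 3 counts and from 17 to 21 points at the blastocyst count. It is nil for a two-level grade and reverses for a non-monotone change.

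These sizes rest on assumed scales, distributions, odds ratios and embryo counts, and on independence of embryos. The powered blastocyst comparison and its 1300 per group are unaffected. This is an optional improvement and not a fault in validity.

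**What to change.** Add to Section 7 that ordered grades kept in more than two levels (the Day 3 grade and the Day 5–7 grades) are compared between arms with a proportional-odds model on arm, with standard errors clustered by patient, reporting the common odds ratio and its 95% CI. State the grade scale in the same place. Keep Chi-squared or Fisher for unordered categories, and tabulate the full grade distribution by arm.

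The cost is a few sentences of SAP wording; sample size, procedures and data collection need not change. The downside is that a single odds ratio can miss a non-monotone shift, and the table is there to show one.
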